9.2. Inclusion Criteria

Subjects who meet all of the following criteria (see Table 9.2-1) may be given consideration for inclusion in this clinical investigation, provided no exclusion criterion (see Section 8.3) is met.

Table 9.2-1: Inclusion Criteria

Clinical Inclusion Criteria	IC1. Study candidate is scheduled to be trialed, on-label, with a commercially approved Boston Scientific neurostimulation system for pain, per local directions for use (DFU)
	IC2. Provides signed, dated, and documented NAVITAS study informed consent on an Institutional Review Board (IRB) - approved informed consent form
	IC3. Is willing and able to comply with completing protocol required assessments and evaluations
	IC4. [REDACTED]
	IC5. [REDACTED]
	IC6. [REDACTED]
	IC7. [REDACTED]
	IC8. [REDACTED]
	IC9. [REDACTED]
	IC10. 18 years of age or older when written informed consent is obtained

Abbreviations: IRB : Institutional Review Board

9.3. Exclusion Criteria

Subjects who meet any one of the following criteria (9.3-1) will be excluded from this clinical study.

Table 9.3-1: Exclusion Criteria

Clinical Exclusion Criteria	[REDACTED]
	EC2. Has any pain-related diagnosis, medical/psychological condition or external factors that, in the investigator's medical judgment, might confound reporting of study outcomes (e.g. history of pelvic pain, anginal pain, chronic migraine, involved in litigation, workmen's compensation)
	[REDACTED]

Abbreviations: BSC : Boston Scientific

10. Subject Accountability

10.1. *Point of Enrollment*

The point of enrollment in the NAVITAS Study is the time at which a subject signs and dates the valid, IRB/EC-approved NAVITAS informed consent form. No NAVITAS study-related procedures or assessments can take place until the NAVITAS informed consent form is signed.

10.2. *Withdrawal*

All subjects enrolled in the NAVITAS clinical study (including those withdrawn from the clinical study or lost to follow-up) shall be accounted for and documented. If a subject withdraws from the NAVITAS clinical investigation, the reason(s) shall be reported. If such withdrawal is due to problems related to device safety or performance, the investigator shall ask for the subject's permission to follow his/her status/condition outside of the NAVITAS clinical study per standard of care.

Reasons for withdrawal include:

- physician discretion,
- subject choice to withdraw consent,
- subject's failure to meet inclusion or exclusion criteria after enrollment,
- failure to receive adequate pain relief during the Neurostimulation Trial,
- implant of a non-BSC neurostimulation system,
- lost to follow-up, or
- death.

[figure not shown]
While study withdrawal is discouraged, subjects may withdraw from the study at any time, with or without reason, and without prejudice to further treatment. In all cases of withdrawal or discontinuation, the Investigator should make reasonable efforts to determine the reason for the subject's withdrawal.

Withdrawn subjects will be followed per the End of Study Action Plan as described in Section 10.5.

All applicable case report forms (CRFs) up to the point of subject withdrawal and an "End of Study" form must be completed. Any subject deemed "lost to follow-up" should have a minimum of three documented attempts to contact him/her prior to completion of the "End of Study" form.

Additional data may no longer be collected after the point at which a subject has been withdrawn from the study or withdraws consent, for whatever reason. All open adverse events should be closed or documented as unresolved. Data collected up to the point of subject withdrawal may be used and analyzed.

Withdrawn subjects will not be replaced.

10.4. *Enrollment Controls*

Enrollment will continue until one of the following events occurs:

- Up to 1,400 subjects are enrolled.
- Up to 960 enrolled subjects receive a permanent neurostimulator implant.
- The study is terminated at any time, at the study sponsor's discretion.

Enrollment controls will be implemented and communicated per the NAVITAS study Enrollment Communication Plan.

10.5. *End-of-Study Action Plan*

[figure not shown]
When each enrolled subject completes the NAVITAS Study, or withdraws, the subject exits the NAVITAS Study. If the subject is implanted, the subject may continue to use the neurostimulator system per the applicable Directions for Use and should be followed according to standard, routine medical care. The chest-worn biosensor, wrist-worn biosensor, study smartphone, and accessories should be returned by subjects who complete or withdraw from the NAVITAS Study to the site.

[figure not shown]
11. Study Methods

[figure not shown]
[REDACTED]

[figure not shown]
[REDACTED]

[figure not shown]
[REDACTED]

11.2. *Study Candidate Screening*

To determine eligibility for enrollment into the NAVITAS Study, the inclusion and exclusion criteria must be assessed. Screening is a process that includes criteria being assessed from the time of informed consent through the Baseline Visit. Subjects who have provided informed consent and who have been determined to not meet all eligibility requirements will be withdrawn. Those inclusion and exclusion criteria that are part of routine care for neurostimulation do not require informed consent. Patients who meet all inclusion criteria (as described in Section 9.2) and do not meet any exclusion criterion (as described in Section 9.3), may be offered participation in the NAVITAS study.

Subjects taking prescription opioids for primary chronic pain complaint (low back and/or leg pain) whose opioid medications are not stable for 30 days following informed consent will be withdrawn however may be reconsented and rescreened once 30 days have passed.

11.3. *Informed Consent*

After a patient has been identified as a potential NAVITAS study candidate, written Informed Consent must be obtained prior to any NAVITAS study related assessments.

- The context of the NAVITAS study must be fully explained to the patient and patients must be given an opportunity to ask questions and have those questions answered to their satisfaction.
- Study personnel should explain to each potential participant that even if he or she agrees to participate in the study and signs an informed consent form, further testing might demonstrate that he or she is not eligible for the study.
- Written informed consent must be recorded appropriately by means of the subject's dated signature.
- The consent process must be documented in the subject's medical chart.

11.4. *Baseline Visit (In-office)*

The NAVITAS study subject Baseline Visit:

- The NAVITAS visit must occur \geq 8 – 14 days prior to Stimulation Trial Procedure for De Novo Cohort subjects.
- This is Day 0 for Existing RELIEF cohort.
- Refer to Table 11.1-1: Data Collection Schedule for visit window and study assessments.

Subjects will be trained on the use of at home devices: a wrist-worn biosensor, a chest-worn biosensor, a pain log and a smart phone/ eDiary Application. Subjects will be instructed to wear

the wrist-worn biosensor, complete the eDiary application and Pain Log daily at home until the 12-Month Visit. Subjects will be asked to bring all devices with them to all follow-up visits.

11.5. *Baseline Period (At Home)*

- Refer to Table 11.1-1: Data Collection Schedule for visit window and study assessments.

11.6. *Neurostimulation Trial Procedure Visit (In-office, Day 0 for De Novo Cohort)*

- De Novo Cohort only
- Refer to Table 11.1-1: Data Collection Schedule for visit window and study assessments.

11.7. *Trial Period (At Home)*

- De Novo Cohort only
- Chest-worn biosensor patch Wrist-worn biosensor, Pain Log, and eDiary application daily during trial period

11.8. *End of Neurostimulation Trial Period Visit (In-office)*

- De Novo Cohort only
- Refer to Table 11.1-1: Data Collection Schedule for visit window and study assessments.

11.9. *IPG Implantation and Activation Visit (In-office)*

- Up to 12 Month Post Neurostimulation Trial Procedure Visit
- Refer to Table 11.1-1: Data Collection Schedule for visit window and study assessments.

11.10. *Month 1, 2, 3 Post Neurostimulation Trial Procedure Visit (De Novo Cohort)/Post Enrollment (Existing Cohort) Period (At Home)*

- Refer to Table 11.1-1: Data Collection Schedule for visit window and study assessments.

11.11. *3-Month Post Neurostimulation Trial Procedure Visit⁴ (De Novo Cohort only) Post Enrollment (Existing Cohort) Visit (In-office, 90 days ± 10 days)*

- Refer to Table 11.1-1: Data Collection Schedule for visit window and study assessments.

11.12. *Month 4, 5, 6 Post Neurostimulation Trial Procedure Visit (De Novo Cohort)/Post Enrollment (Existing Cohort) Period (At Home)*

- Refer to Table 11.1-1: Data Collection Schedule for visit window and study assessments.

⁴ Only for De Novo cohort subjects who have undergone IPG Implantation prior to this visit

11.13. 6-Month Post Neurostimulation Trial Procedure Visit (De Novo Cohort Existing Cohort, as applicable)

- Refer to Table 11.1-1: Data Collection Schedule for visit window and study assessments.

11.14. Month 7, 8, 9 Post Neurostimulation Trial Procedure Visit (De Novo Cohort)/ Post Enrollment (Existing Cohort) Period (At Home)

- Refer to Table 11.1-1: Data Collection Schedule for visit window and study assessments.

11.15. 9-Months Post Neurostimulation Trial Procedure Visit⁴ (De Novo Cohort only, In-office, 270 days ± 30 days)

- Refer to Table 11.1-1: Data Collection Schedule for visit window and study assessments.

11.16. Month 10, 11, 12 Post Neurostimulation Trial Procedure Visit (De Novo Cohort)/ Post Enrollment (Existing Cohort) Period (At Home)

- Refer to Table 11.1-1: Data Collection Schedule for visit window and study assessments.

11.17. 12-months Post Neurostimulation Trial Procedure (De Novo and Existing, as applicable) (In-office, 365 ± 60 days Post Neurostimulation Trial Procedure Visit)/Post Enrollment (Existing) Visit (In-office, 365 ± 60 days)

- Refer to Table 11.1-1: Data Collection Schedule for visit window and study assessments.
- NAVITAS (De Novo and Existing) Subjects may end study participation after this visit or elect to continue with Navitas optional visits and at home activities.

11.18. Months 13-24 Post Neurostimulation Trial Procedure Visit Period (Optional De Novo and Optional Existing Cohort⁵) Period (At Home)

- Refer to Table 11.1-1: Data Collection Schedule for visit window and study assessments.

11.19. Optional 24-months Post Neurostimulation Trial Procedure Visit⁵ (In-office, 720 ± 60 days Post Neurostimulation Trial Procedure Visit)

- Refer to Table 11.1-1: Data Collection Schedule for visit window and study assessments.

11.20. Months 25-36 Post Neurostimulation Trial Procedure Visit Period (Optional De Novo and Optional Existing Cohort⁶) Period (At Home)

- Refer to Table 11.1-1: Data Collection Schedule for visit window and study assessments.

⁵ NAVITAS assessments optional only for Subjects that have not ended study participation and opted to continue NAVITAS Study follow up for > 12 months

11.21. *Optional 36-months Post Neurostimulation Trial Procedure Visit⁵(In-office, 1095 ± 60 days Post Neurostimulation Trial Procedure Visit)*

- Refer to Table 11.1-1: Data Collection Schedule for visit window and study assessments.

11.22. *Unscheduled Study Visits*

Subjects may have unscheduled study visits as needed for device related visits (e.g., reprogramming, replacement, revision) or evaluation of adverse events. Refer to Table 11.1-1: Data Collection Schedule for visit window and study assessments.

11.23. *Study Completion*

An enrolled subject may complete participation in the NAVITAS Study in one of several ways:

- De Novo subjects experiencing a negative trial complete the study at the End of the Neurostimulation Trial Period visit; or in case of Permanent trials, after the trial lead(s) explant surgery.
- De Novo subjects who experienced a successful trial but do not receive a permanent implant within 12 months complete the study at the 12-months Post Neuromodulation Trial Visit.
- Existing Subjects that complete the study at the 12-months Post Enrollment Visit and decide not to continue with optional follow-up.
- De Novo Subjects that complete the study at the 12-months Post Neurostimulation Trial Visit and decide not to continue with optional follow-up.
- Subjects who withdraw, die, or become lost to follow up are considered to have exited the NAVITAS Study. Withdrawn subjects will not be replaced.
- Subjects who complete their 36-Months Post Neurostimulation Trial Procedure Visit.

After each subject completes the NAVITAS Study, medical care will continue per local treatment protocols.

11.24. *Source Documents*

See below Source Documentation Requirements for NAVITAS study source documentation requirements

Table 11.24-1: Source Documentation Requirements

Requirement	Disposition
Informed Consent Form and Consent Process Documentation	Retained at study site
Inclusion and Exclusion Criteria Documentation	Retained at study site
Saliva related collection and transmission	Retained at study site or analysis vendor

Table 11.24-1: Source Documentation Requirements

Requirement	Disposition
Imaging (MRI/CT/Fluoroscopy)	Retained at study site
Medical Records	Retained at study site
SCS Data	Electronic data collection platform/EDC
NAVITAS Study Questionnaires (in-office)	Retained at study site and/or electronic data collection platform / EDC
Technical Source Forms or other source documentation worksheets	Retained at study site
Chest-worn biosensor data	Retained in secure data server
Wrist-worn biosensor data	Retained in secure data server
Pain Log	Retained in secure data server
eDiary application Questionnaires data	Retained in secure data server
eDiary application Voice Recordings	Retained in secure data server

12. Statistical Considerations

12.1. *Endpoints*

12.1.1. Exploratory Endpoints

This study does not have any pre-defined endpoints but may include ad-hoc exploratory endpoint(s) to explore the relationship between metrics and clinical outcomes

Exploratory endpoint(s) will be intended to generate hypotheses for future studies. Consequently, no correction for multiple testing will be performed for exploratory endpoint(s). Any exploratory endpoint(s) will be clearly identified as such in study reports, as applicable.

12.1.1.1. Hypotheses

There are no formal hypotheses for this study.

12.1.1.2. Sample Size

Sample size calculations for this exploratory study were calculated based an estimate of the number of subjects required to obtain a saturated level of model performance in prediction of pain scores in a subgroup given a set of covariate parameters.

[REDACTED]

[REDACTED]

[REDACTED]

[REDACTED]

12.1.1.3. Statistical Methods

Univariate and multivariable models will be used to determine correlations between neurostimulation treatment parameters on clinical outcomes.

Data from all eligible patients will be used for analysis. Subgroup/cohort analyses will be defined by demographics, pain diagnosis, treatment parameters, treatment efficacy and medication use.

Missing data from biosensors will not be imputed. A sensitivity analysis using LOCF imputation of clinical outcomes will be completed. [REDACTED]

12.2. *General Statistical Methods*

[REDACTED]

[REDACTED]

[REDACTED]

[REDACTED]

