The NAVITAS Sub-study is being conducted under the RELIEF Study however subjects enrolled in NAVITAS will follow protocol requirements within this document only. Subjects enrolled in the NAVITAS protocol will not be enrolled in the RELIEF study and should be withdrawn from RELIEF if they are already enrolled.

[figure not shown]
NAVITAS: A Study to Characterize the Relationship between Select Objective Metrics and Clinical Outcomes in Chronic Pain Patients treated with Boston Scientific Neurostimulation Systems

[figure not shown]
The NAVITAS Sub-study is being conducted under the RELIEF Study however subjects enrolled in NAVITAS will follow protocol requirements within this document only. Subjects enrolled in the NAVITAS protocol will not be enrolled in the RELIEF study and should be withdrawn from RELIEF if they are already enrolled.

[figure not shown]
Statistical Methods	
Exploratory Statistical Methods	Univariate and multivariable models will be used to determine correlations in neurostimulation treatment effects on clinical outcomes
Sample Size Parameters	Sample size calculations for this exploratory study were calculated using an empirical analysis of current RELIEF data based an estimate of the number of subjects required to obtain a saturated level of model performance in prediction of pain scores in a subgroup given a set of covariate parameters.  

[figure not shown]

4. Introduction

NAVITAS Sub-study is being conducted under the RELIEF Study however subjects enrolled in NAVITAS will follow protocol requirements within this document only. Subjects enrolled in the NAVITAS protocol will not be enrolled in the RELIEF study and should be withdrawn from RELIEF if they are already enrolled.

4.1. *Chronic Intractable Pain*

Chronic intractable pain is often defined as pain persisting for at least 6 months which has not responded to conservative treatment(s). The pain may be due to current or past nerve injury and causes significant disability, reduced work productivity, reduced quality of life, and significant cost burden.

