Traditionally, Spinal Cord Stimulation (SCS) has relied on the understanding that to achieve pain relief, dorsal column stimulation-induced paresthesia has to be generated around the area of pain in order to successfully treat pain [7]. However, recent studies indicate that effective pain relief may be obtained by employing stimulation without paresthesia ([8], [9], [10]).

4.3. *Biosensors*

Researchers have explored the idea that pain results in an imbalance of the autonomic nervous system. Thus detecting changes in autonomic tone through the use of biosensors may allow better prediction of pain status [11, 12, 13, 14, 15, 16, 17, 18, 19]. For example, heart rate variability could serve as a measure of stress and changes in perception of pain over time in patients diagnosed with chronic pain. Additional variables such as respiratory rate and activity, including motion, orientation, and sleep could also provide insight into changes in pain status.

5. Device Description

The study includes all commercially approved Boston Scientific neurostimulation systems indicated for the treatment of chronic pain, with the exception of Precision™ and Precision™ Plus, and commercially approved VitalConnect™ Sensor, indicated for continuous collection of physiological data in home and healthcare settings which is used with the physIQ VitaLink Solution.

5.1. *Boston Scientific Neurostimulator Systems (Commercial Device part of Standard of Care)*

Refer to the Directions for Use for detailed device description.

5.2. *PhysIQ VitaLink Solution*

The physIQ VitaLink Solution (“Platform”) is a commercially available wireless remote monitoring system intended for use by healthcare professionals for continuous collection of physiological data in home and healthcare settings. The Platform consists of a VitalConnect Sensor (“chest-worn biosensor patch”), mobile application for data transmission, cloud-based IT infrastructure, and physiology analytics engine. The VitalConnect Sensor is a battery-operated adhesive patch with integrated sensors and a wireless transceiver. It is worn on the torso and measures and records physiological variables that can include, but are not limited to, electrocardiography (ECG) and activity. Data are transmitted wirelessly from the VitalConnect Sensor for storage and analysis. Subjects are provided the following commercial products with the VitalConnect Sensor:

- WEBCOL/Curity Alcohol Prep Pads,
- UNI-SOLVE Adhesive Remover Wipes

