- Smartphone and charger

6. Study Objectives

The objective of the NAVITAS study is to characterize the relationship between select objective metrics and clinical outcomes in chronic pain patients treated with Boston Scientific commercially approved neurostimulation systems.

7. Study Endpoints

This study does not have any pre-defined endpoints but may include ad-hoc exploratory endpoint(s) to explore the relationship between metrics and clinical outcomes. Exploratory endpoint(s) will be intended to generate hypotheses for future studies.

[figure not shown]
Consequently, no correction for multiple testing will be performed for exploratory endpoint(s). Any exploratory endpoint(s) will be clearly identified as such in study reports, as applicable.

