Exploratory endpoint(s) will be intended to generate hypotheses for future studies. Consequently, no correction for multiple testing will be performed for exploratory endpoint(s). Any exploratory endpoint(s) will be clearly identified as such in study reports, as applicable.

7. Study Design

The study is a prospective, post-market, multi-center study for chronic pain.

7.1.

Please see below study design.

Figure 7.1-1: ENVISION Study Design

Additional Study Visits for SCS device related activities (e.g. SCS trial, end of SCS trial, IPG implant, IPG Activation, reprogramming, revision, etc.) or as needed for study

[figure not shown]

Figure 7.1-1: ENVISION Study Design for Extension Cohort

7.2. *Treatment Assignment*

Consecutive eligible patients who consent to participation and have met all the inclusion and none of the exclusion criteria will be enrolled.

7.2.1. **Treatment**

The study treatment will consist of neurostimulation trial therapy with any commercially approved Boston Scientific neurostimulator for pain. Individualization of neurostimulation therapy for pain will be determined according to investigator discretion and site routine care, and in accordance with inclusion and exclusion criteria.

7.3. *Justification for the Study Design*

All devices used in this study are approved for commercial release.

This study is designed to gather data which will be analyzed to characterize the relationship between select objective metrics and clinical outcomes in chronic pain patients treated with Boston Scientific commercially approved neurostimulation systems.

A prospective study design will eliminate the bias associated with case selection in a retrospective review and will ensure that identical procedures are followed for data capture and review.

A multi-center design will minimize the impact on treatment outcome that may potentially result from differences in patient selection, regional differences in the patient demographic, and differences in investigator technique and patient management.

8. Subject Selection

8.1. *Study Population and Eligibility*

Subjects enrolled in this study will be established patients in a medical practice (e.g. pain management, surgical, physical medicine and/or rehabilitation) who are planning to receive or have received a commercially approved Boston Scientific neurostimulation system are eligible to receive neurostimulation therapy to treat their pain condition.

8.2. *Inclusion Criteria*

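### Do the stated models miss the objective by naming stimulation parameters instead of objective metrics, and does an undefined efficacy subgroup bias the results?

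*Combined protocol and SAP*

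**What the plan says.** The objective, in NAVITAS section 6 and ENVISION section 6, is to "characterize the relationship between select objective metrics and clinical outcomes in chronic pain patients". ENVISION 7.3 repeats it as the reason for the design: "This study is designed to gather data which will be analyzed to characterize the relationship between select objective metrics and clinical outcomes". NAVITAS 4.3 gives the idea behind the sensors: "detecting changes in autonomic tone through the use of biosensors may allow better prediction of pain status".

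The model sentence in NAVITAS 12.1.1.3 and ENVISION 11.1.1.3 reads "Univariate and multivariable models will be used to determine correlations between neurostimulation treatment parameters on clinical outcomes". The NAVITAS synopsis words it differently: "Univariate and multivariable models will be used to determine correlations in neurostimulation treatment effects on clinical outcomes".

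NAVITAS 12.1.1.1 and ENVISION 11.1.1.1 state that there are no formal hypotheses. NAVITAS 12.1.1 adds that the study "may include ad-hoc exploratory endpoint(s) to explore the relationship between metrics and clinical outcomes", and ENVISION 11.1.1 says much the same. On populations and subgroups, both methods sections state "Data from all eligible patients will be used for analysis" and "Subgroup/cohort analyses will be defined by demographics, pain diagnosis, treatment parameters, treatment efficacy and medication use".

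**The concern.** Two things look wrong.

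First, the explanatory side of the only visible model sentence is stimulation settings (or, in the NAVITAS synopsis, treatment effects), whereas the objective concerns objective metrics, which NAVITAS 4.3 and ENVISION 4.3 suggest are mainly sensor signals. Taken literally, the named models would not estimate the relationship the study exists to describe. That relationship would rest on optional ad-hoc work, although subjects carry daily sensor, pain-log and diary duties to provide the data.

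Second, treatment efficacy is known only after stimulation begins, and it has no visible measure, cut-off or time point. It could be the clinician's end-of-trial judgement (NAVITAS 13.2.17) or percent pain relief (NAVITAS 13.2.26). If it is nearly the same thing as the modelled pain outcome, selecting on it narrows the outcome's range, and a correlation inside the subgroup can shrink for that reason alone. ENVISION raises the stakes because observed relationships may be used to make recommendations.

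**Working it through.** **Part 1: which analyses the text supports.** There is no figure to reproduce. The check is to read the model sentence against the statistical text around it.

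- NAVITAS 12.1.1.3 and ENVISION 11.1.1.3 state, in the same sections as the model sentence, that missing biosensor data will not be imputed. That rule has a purpose only if biosensor data enter the analyses.
- NAVITAS 12.1.1.2 and the synopsis base the sample size on how many subjects are needed for a pain-score prediction model to stop improving, given a set of covariates. A prediction model for pain is therefore planned, although the visible text does not name its covariates.
- NAVITAS 12.1.1 and ENVISION 11.1.1 name the metric-outcome relationship as the subject of the exploratory endpoints.
- A redaction directly follows the NAVITAS methods text, and General Statistical Methods is blacked out in both protocols. Visible numbering also jumps from 12.3 to 12.3.6 in NAVITAS and from 11.3 to 11.3.6 in ENVISION. Model terms or a definition of efficacy may sit in text that is not shown.

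**Part 2: what selection on efficacy does to a correlation.** Inputs, all assumed because the documents give none:

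- ρ, the metric-outcome correlation in the full sample;
- c, the efficacy-outcome correlation;
- d, the metric-efficacy correlation;
- v, the variance of standardised efficacy within the selected group. For the upper half of a normal distribution v = 1 - 2/π = 0.363, so 1 - v = 0.637.

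With trivariate normality and one value per subject, the subgroup correlation is

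r′ = [ρ - (1 - v)·c·d] / √{[1 - (1 - v)·d²]·[1 - (1 - v)·c²]}

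*Case A: the metric relates to efficacy only through the outcome, so d = c·ρ.* The formula reduces to r′ = ρ√k / √[1 - (1 - v)c²ρ²], with k = 1 - (1 - v)c². For ρ = 0.50 and c = 1: 0.50 × √0.363 / √(1 - 0.637 × 0.25) = 0.301/0.917 = 0.33.

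| c | r′ when ρ = 0.50 | r′ when ρ = 0.30 |
|---|---|---|
| 1 (same variable) | 0.33 | 0.19 |
| 0.8 | 0.41 | 0.24 |
| 0.6 | 0.45 | 0.27 |
| 0.5 | 0.47 | 0.28 |
| 0.3 | 0.49 | 0.29 |

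The loss is large only when efficacy is almost the modelled outcome itself.

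*Case B: let d vary, with ρ = 0.30 and c = 0.5.* The outcome term is √(1 - 0.637 × 0.25) = 0.917.

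- d = 0.3: (0.30 - 0.637 × 0.15)/(0.971 × 0.917) = 0.204/0.890 = 0.23
- d = 0: 0.30/0.917 = 0.33
- d = -0.2: (0.30 + 0.637 × 0.10)/(0.987 × 0.917) = 0.364/0.905 = 0.40

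The subgroup value can fall below or rise above 0.30.

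*Case C: repeated measures.* NAVITAS collects wrist-sensor and pain-log data daily up to the 12-month visit (section 11.4). If the correlation of interest is within subjects and subjects are split on their mean outcome, each subject's deviations from that mean are independent of the split under a normal model. A simulation with a within-subject correlation of 0.50 and a median split returned 0.50 in the selected half.

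**The case for a change.** The best case for a change is that the wording really does diverge from the objective, in three places and in two different versions, and that aligning it would cost a few words. Stimulation settings and sensor data are treated as separate sources in both protocols (NAVITAS 11.24; ENVISION 12.4.20 and 12.4.22), so reading one as the other is strained. ENVISION 11.1.1.3 leaves further analysis detail to the study reports, so choices could be settled after the data are seen. The rule that changes to planned analyses be documented protects little where the plan is thin. On efficacy, NAVITAS subjects with a negative trial leave after the trial period (11.23), and ENVISION subjects leave 7 to 30 days after it (10.10). End-of-trial candidacy would therefore leave few or no non-responders with later follow-up among trialled subjects. That pushes the definition towards follow-up pain relief, where overlap with the outcome is greatest.

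The textual point stands: the sentences are loose and the synopsis does not match the body. The likely overlap stands as a possibility. Neither shows a wrong analysis. Analyses of stimulation parameters also suit ENVISION's therapy-optimisation rationale (4.3), so that sentence describes a legitimate question there. Late choices are declared openly: both protocols disclaim pre-defined endpoints, label such results exploratory and direct them at generating hypotheses. Classifying response at an earlier visit and analysing only later data would discard data. If earlier response correlates 0.5 to 0.8 with the later outcome (assumed), Case A still gives 0.47 to 0.41 for a true 0.50, so the gain is debatable.

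**Conclusion.** No change to the plan is called for. The model sentences are imprecise, but the biosensor missing-data rule, the NAVITAS pain-prediction basis for sample size and the endpoint text make the intended metric-outcome analyses clear enough for an analyst to carry out. Redaction prevents any firm claim that the model or the efficacy definition is absent.

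The subgroup effect has no determinate size or sign. Under one set of assumptions (between-subject, one value per subject, median split, metric linked to efficacy only through the outcome) a correlation of 0.50 reads between 0.33 and 0.49 for c from 1 to 0.3. Under others the subgroup value is unchanged or larger. Analyses of all eligible patients are unaffected.

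With no hypotheses and no powered endpoints, nothing confirmatory turns on this. An analyst would in any case name the metrics as model terms and state how efficacy was defined when reporting such subgroups. This judgement would be weaker if efficacy-subgroup correlations alone were used to support the recommendations ENVISION allows, but nothing in the visible text says that they would be.
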